3.5. Subject Inclusion Criteria

Subjects enrolled into this study must meet the following inclusion criteria to be eligible.

1. Histopathologically-confirmed diagnosis of cancer that is metastatic or unresectable at Screening.
 - Subjects with metastatic or locally and/or regionally advanced unresectable CSCC.
Note 1: CSCC subjects without radiographically measurable disease are not excluded if there is at least 1 lesion ≥ 10 mm in at least 1 dimension documented by color photography.
Note 2: Subjects with tumors that arise in the setting of chronic inflammation (Marjolin's ulcer) such as chronic wounds and/or scars are excluded.
 - **Cohort A1:** Subjects who have not received prior systemic therapy for CSCC and who are not eligible for curative radiation.
 - **Cohort A2:** Subjects who have progressed while receiving a PD-1-blocking antibody or within 12 weeks of discontinuation. PD-1-blocking antibody treatment may have been administered in the adjuvant and/or neoadjuvant and/or locally advanced or metastatic setting.
 - Subjects with metastatic or locally and/or regionally advanced unresectable MCC.
Note: MCC subjects without radiographically measurable disease are not excluded if there is at least 1 lesion ≥ 10 mm in at least 1 dimension documented by color photography./

- **Cohort B1:** Subjects who have not received prior systemic therapy for MCC.
- **Cohort B2:** Subjects who have progressed while receiving a PD-1-blocking antibody or within 12 weeks of discontinuation. PD-1-blocking antibody treatment may have been administered in the adjuvant and/or neoadjuvant and/or locally advanced or metastatic setting.
- **Cohorts C1 and C2:** Previously treated subjects with advanced or metastatic TNBC must have disease that is HER2-negative, estrogen and progesterone receptor-negative, or < 5% expression based on American Society of Clinical Oncology/College of American Pathologists guidelines ([Hammond, 2010a](#))[\(Hammond, 2010b\)](#)[\(Wolff, 2013\)](#). Subjects with disease recurrence or progression following neoadjuvant or adjuvant therapy are eligible. Subjects with advanced or metastatic disease may have up to 5 lines of systemic therapy. Patients must have previously received treatment with sacituzumab govitecan (all TNBC patients), with trastuzumab deruxtecan (HER2-low patients) and with PARP inhibitor (for BRCA) patients.
 - **Cohort C1:** Subjects who have not received prior therapy with iCPIs.
 - **Cohort C2:** Subjects who have progressed while receiving a PD-1-blocking antibody or within 12 weeks of discontinuation.
- **Cohort D:** Advanced BCC subjects (metastatic or locally advanced) who are not candidates for curative surgery and have not received prior therapy with a hedgehog pathway inhibitor (vismodegib or sonidegib) or prior anti-PD-1/PD-L1 therapy and who do not wish to receive or who are not candidates for a hedgehog inhibitor.

Note: BCC subjects without radiographically measurable disease are not excluded if there is at least 1 lesion ≥ 10 mm in at least 1 dimension documented by color photography.
- **Cohort E (not conducted in Europe):** Advanced non-small cell lung cancer (NSCLC) subjects (locally advanced who are not candidates for surgical resection or definitive chemoradiation or metastatic) whose tumors have high PD-L1 expression (TPS $\geq 50\%$) based on a prior PD-L1 result as determined by a CAP/CLIA (or equivalently licensed) lab, with no EGFR, ALK or ROS1 aberrations, and who have not received prior anti-PD-1/PD-L1 therapy and are amenable to IT therapy and do not wish to receive chemotherapy.
- **Cohort F:** R/M Oropharyngeal squamous cell carcinoma (OPSCC) subjects with PD-L1 CPS score ≥ 1 , HPV-positive disease who have not received prior systemic therapy for R/M disease. HPV-positive status, based on a prior result, must be established in a surgical specimen or a core biopsy specimen from any site of OPSCC (primary site, nodal site, and/or distant metastatic site, either at time of diagnosis or later) in a CAP/CLIA (or equivalently licensed) lab, as follows:
 - For subjects with documented history of oropharynx primary disease, either of the following will be accepted as evidence of HPV-positive OPSCC: positive p16 immunohistochemistry (IHC) or positive HPV DNA or RNA in situ hybridization (ISH).

- For subjects with HNSCC of unknown primary, positive HPV DNA or RNA ISH is required as evidence of HPV-positive disease.
- PD-L1 expression (CPS ≥ 1) is based on a prior PD-L1 result as determined by CAP/CLIA (or equivalently licensed) lab.

2. Measurable disease, as defined by RECIST v1.1 and all of the following:
 - At least 1 accessible lesion amenable to repeated IT injection.
 - A previously irradiated lesion may be used as a target lesion if subsequent disease progression in that lesion (at least 20% increase in dimensions with a 5 mm absolute increase) was documented.
3. Able to provide tissue from a core or excisional/incisional biopsy (fine needle aspirate is not sufficient). A newly obtained biopsy (within 90 days before the start of study treatment) is preferred but an archival sample is acceptable if no intervening therapy was received.

Note: Refer to the laboratory manual for tissue sampling details.
4. Adequate organ function based on most recent laboratory values within 3 weeks before first dose of study treatment on W1D1:
 - Bone marrow function:
 - neutrophil count $\geq 1500/\text{mm}^3$
 - platelet count $\geq 100,000/\text{mm}^3$
 - hemoglobin concentration $\geq 9 \text{ g/dL}$
 - Liver function:
 - total bilirubin ≤ 1.5 times the upper limit of normal (ULN) with the following exception: subjects with Gilbert Disease total serum bilirubin ≤ 3 times ULN
 - aspartate aminotransferase and alanine aminotransferase ≤ 3 times the ULN
 - Renal function: estimated (Cockcroft-Gault) or measured creatinine clearance $\geq 30 \text{ mL/min}$
 - Coagulation:
 - International normalized ratio (INR) or prothrombin time (PT) ≤ 1.5 times ULN unless subject is receiving anticoagulant therapy, as long as PT or partial thromboplastin time (PTT) is within therapeutic range of intended use of anticoagulants.
 - Activated partial thromboplastin time or PTT ≤ 1.5 times ULN unless subject is receiving anticoagulant therapy, as long as PT or PTT is within therapeutic range of intended use of anticoagulants.
5. Age ≥ 18 years at time of consent.
6. Eastern Cooperative Oncology Group (ECOG) Performance Status of 0 to 1 at Screening.
7. Capable of understanding and complying with protocol requirements.

8. Criterion removed in Amendment 3.
9. Able and willing to provide written informed consent and to follow study instructions. Subjects unable to provide written informed consent on their own behalf will not be eligible for the study.

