Similar progress was made in the treatment of metastatic MCC, where PD-1/PD-L1-blocking antibodies have demonstrated objective response rates 39-56% in treatment-naïve subjects ([Nghiem, 2016](#))([Nghiem, 2018](#))([D'Angelo, 2018](#)). For recurrent MCC, a case report describes a partial response to recombinant interferon- α 2a + topical imiquimod cream ([Wahl, 2016](#)). In the dose escalation portion of the phase 1 study of TLR9 agonist cavrotolimod in combination with pembrolizumab, 2 objective responses were observed in advanced MCC subjects with prior disease progression during or after prior anti-PD-1 therapy. Therefore, the combination of cemiplimab + vidutolimod is an appropriate study option for MCC subjects in both the PD-1 naïve and PD-1 resistant settings.

Basal Cell Carcinoma (BCC)

For subjects with locally advanced BCC, orally administered hedgehog pathway inhibitors (HHIs) such as vismodegib and sonidegib produce objective response rates of 48-56% in pivotal studies ([Sekulic, 2015](#))([Dummer, 2016](#)), and the reported response rate for vismodegib in the real-world setting is 68% ([Basset-Seguin, 2017](#)). However, these treatments are associated with adverse events such as muscle spasms, dysgeusia, alopecia, and weight decrease. Because approximately half of advanced BCC subjects do not respond to HHIs, and because the safety profile of these agents can be difficult for some subjects, new treatment options are needed.

BCC has similar clinical risk factors as CSCC and is also a hypermutated tumor ([Chalmers, 2017](#))([Yarchoan, 2017](#))([Nehal, 2018](#)). Cemiplimab produces an ORR of 31% in locally advanced BCC subjects in the second line after HHI inhibitors and is approved therapy in this setting ([Stratigos, 2021](#)).

Vidutolimod merits study in BCC for several reasons. As with CSCC, it is a tumor type that is responsive to interferon- α ([Chimenti, 1995](#)). In a pilot study of the TLR9 agonist PF-3512676, local regressions were observed in all 5 BCC subjects, including four partial regressions and one complete regression ([Hofmann, 2008](#)). The topical TLR7 agonist imiquimod, which also induces production of Type 1 interferons, is approved therapy for superficial BCC but not for advanced BCC ([Geisse, 2002](#)). Therefore, the combination of vidutolimod + cemiplimab could enhance the activity of single agent cemiplimab in the first line setting and is of interest as an investigational option for advanced BCC subjects.

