1.3.3.3. Non-Small Cell Lung Cancer (NSCLC)

Immune checkpoint inhibitors have revolutionized the treatment of NSCLC. PD-L1 is an important biomarker for selection of subjects more likely to respond to immunotherapy. Among subjects with newly diagnosed advanced NSCLC with PD-L1 CPS of at least 50% and without EGFR, ALK, or ROS1 genomic alterations, cemiplimab has demonstrated durable objective response rate (ORRs) of approximately 40% and superiority over chemotherapy in improving progression-free survival and overall survival ([Sezer, 2021](#)). Other checkpoint inhibitors (pembrolizumab, atezolizumab) have also demonstrated improved efficacy compared to platinum-based chemotherapy, as first line monotherapy in advanced NSCLC patients with high PD-L1 expression (CPS $\geq 50\%$) ([Reck, 2016](#))([Herbst, 2020](#)). In terms of OS, Cemiplimab ranked highest compared to atezolizumab and pembrolizumab ([Majem, 2021](#)). However, there are limited non-chemotherapy treatment options for subjects PD-L1 high NSCLC subjects who do not respond or progress after the initial response to anti-PD-1 therapy.

A clinical trial (CMP-001-003) has evaluated vidutolimod in combination with atezolizumab with and without radiation therapy in subjects with PD-1/PD-L1 blockade-resistant NSCLC ([Negrao, 2022](#)). On this study, intratumoral injections of vidutolimod were administered safely and successfully, including injection of visceral lesions.

No objective responses were observed in this heavily pretreated NSCLC patient population, but two subjects had tumor shrinkage (<30% decrease in tumor size, nonirradiated) and this correlated with strong induction of CXCL10. Study CMP-001-003 demonstrated the feasibility of IT therapy in NSCLC, and the lack of efficacy in the PD-1 refractory setting does not preclude possible meaningful antitumor activity in immunotherapy naïve patients. Vidutolimod in combination with standard cemiplimab warrants further development and evaluation in NSCLC in the favorable population of newly diagnosed advanced NSCLC patients with high PD-L1 expression ($\geq 50\%$), with disease that is amenable to IT injections.

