3. INVESTIGATIONAL PLAN

3.1. Overall Study Design

This is a multicenter, open-label, Phase 2 clinical study of vidutolimod administered by IT injection in combination with cemiplimab IV in subjects with selected types of advanced or metastatic cancer with or without prior PD-1-blocking antibody treatment, as follows:

- Cohorts A1 and A2: Subjects with metastatic or locally and/or regionally advanced unresectable CSCC:
 - **Cohort A1:** Subjects who had not received prior systemic therapy for CSCC and who are not eligible for curative radiation
 - **Cohort A2:** Subjects who have progressed while receiving a PD-1-blocking antibody or within 12 weeks of discontinuation
- Cohorts B1 and B2: Subjects with metastatic or locally and/or regionally advanced unresectable MCC:
 - **Cohort B1:** Subjects who had not received prior systemic therapy for MCC
 - **Cohort B2:** Subjects who have progressed while receiving a PD-1-blocking antibody or within 12 weeks of discontinuation
- Cohorts C1 and C2: Previously treated subjects with advanced or metastatic TNBC. Patients must have previously received treatment with sacituzumab govitecan (all TNBC patients), with trastuzumab deruxtecan (HER2-low patients) and with PARP inhibitor (for BRCA) patients:
 - **Cohort C1:** Subjects who had not received prior therapy with immune checkpoint inhibitors (iCPIs)
 - **Cohort C2:** Subjects who have progressed while receiving a PD-1-blocking antibody or within 12 weeks of discontinuation
- **Cohort D:** Subjects with newly diagnosed metastatic or locally and/or regionally advanced unresectable basal cell carcinoma (BCC) who have not received prior hedgehog pathway inhibitor therapy or prior anti-PD-1/PD-L1 therapy and who do not wish to receive or who are not candidates for a hedgehog inhibitor.
- **Cohort E (not conducted in Europe):** Advanced non-small cell lung cancer (NSCLC) subjects (locally advanced who are not candidates for surgical resection or definitive chemoradiation or metastatic) whose tumors have high PD-L1 expression (tumor proportion score [TPS] $\geq 50\%$) based on a prior PD-L1 result as determined by CAP/CLIA (or equivalently licensed) lab, with no EGFR, ALK, or ROS1 aberrations, and who have not received prior anti-PD-1/PD-L1 therapy and are amenable to IT therapy and do not wish to receive chemotherapy.

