8.1. Sample Size Justification

The study is conducted as an exploratory trial. Each cohort of A1, A2, B1, B2, C1, C2, D, E, and F, will enroll approximately 25 subjects. The total number of subjects to be enrolled into this study is approximately 225. Based on historical data, the ORR of available treatment for each disease in Cohort is listed in [Table 12](#). If the observed ORRs in these Cohorts A1, A2, B1, B2, C1, C2, D, E, and F are as listed in [Table 12](#), then the lower bound of 90% confidence interval of ORR is listed in the table below.

Table 12: ORR of Available Treatment by Cohort

Cohort	ORR of Available Treatment	Observed ORR ≥	Lower Bound of 90% Confidence Interval
A1	50%	72%	>50%
A2	<10%	24%	>10%
B1	50%	72%	>50%
B2	<10%	24%	>10%
C1	21%	40%	>21%
C2	<10%	24%	>10%
D	50%	72%	>50%
E	39%	60%	>39%
F	19%	40%	>21%

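### Cohort E's 39% benchmark appears to come from newly diagnosed NSCLC, but its eligibility wording admits subjects already given chemotherapy for advanced disease

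*Protocol*

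**What the plan says.** **Cohort E, rationale.** Protocol Section 1.3.3.3 reports that cemiplimab has shown a "durable objective response rate (ORRs) of approximately 40" percent in newly diagnosed advanced NSCLC with high PD-L1 expression. It says the combination warrants evaluation "in the favorable population of newly diagnosed advanced NSCLC patients with high PD-L1 expression".

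**Cohort E, sizing.** Section 8.1 says each cohort "will enroll approximately 25 subjects". Table 12 gives Cohort E an ORR of available treatment of 39%, an observed ORR of at least 60%, and a lower 90% confidence bound above 39%.

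**Cohort E, eligibility.** Section 3.5 requires advanced, PD-L1-high, driver-negative NSCLC in subjects "who have not received prior anti-PD-1/PD-L1 therapy and are amenable to IT therapy and do not wish to receive chemotherapy". The synopsis, Section 3.1 and SAP Section 2.1 use the same criterion.

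**Other untreated cohorts.** In Section 3.5, A1 and B1 exclude any prior systemic therapy for the disease. Cohort F takes subjects "who have not received prior systemic therapy for R/M disease".

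**Cohort D.** Section 3.1 describes "Subjects with newly diagnosed metastatic or locally and/or regionally advanced unresectable basal cell carcinoma", and Section 1.3.3.1 says the combination "could enhance the activity of single agent cemiplimab in the first line setting". Section 3.5, the synopsis and SAP Section 2.1 do not say newly diagnosed; they bar prior hedgehog inhibitors and prior anti-PD-1/PD-L1 therapy.

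**The concern.** There is no control arm, so the Table 12 benchmark is the only yardstick for Cohort E. It informs the reader only if the enrolled subjects resemble those who produced it. The rationale and, apparently, the benchmark concern newly diagnosed disease. The criterion concerns disease not yet treated with one drug class.

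A subject who received platinum chemotherapy for metastatic NSCLC and never an anti-PD-1/PD-L1 agent satisfies the Cohort E wording. Not wishing to receive chemotherapy now does not bar having received it before. If such subjects enter, the ORR expected without vidutolimod is no longer the 39% in the table, and the observed ORR answers a blurred version of the first-line question.

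**Working it through.** **1. Does anything else close the gap?** Section 6.1.2 makes Sections 3.5 and 3.6 the eligibility test. In Section 3.6, criterion 20 covers only investigational anticancer therapy or devices within 30 days, and criterion 5 requires only recovery from the adverse events of prior treatment. No criterion bars earlier chemotherapy.

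**2. The plan's own figure.** The plan states that if the observed ORRs are as listed, "then the lower bound of 90% confidence interval of ORR is listed in the table below". The inputs are n = 25 and 60%, which is 15/25. The exact (Clopper-Pearson) two-sided 90% lower limit is the 5% quantile of Beta(x, n − x + 1):

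- x = 15: Beta(15, 11) gives 41.7%, above 39% as stated.
- x = 14: Beta(14, 12) gives 37.9%, below 39%.

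Table 12 reproduces, and 15 is the smallest count that clears the benchmark. For X ~ Binomial(25, p), P(X ≥ 15) is 2.7% at p = 0.39 and 58.6% at p = 0.60.

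**3. Effect of pretreated subjects when the combination works.** Let s be the pretreated share and r their ORR on the combination. The documents give neither, so both are assumed. The first-line ORR is set at 60%:

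m = (1 − s) × 0.60 + s × r, and the chance is P(X ≥ 15 | 25, m).

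| r | s = 10% | s = 20% | s = 30% |
|---|---|---|---|
| 50% | m = 0.590: 54.5% | m = 0.580: 50.4% | m = 0.570: 46.4% |
| 35% | m = 0.575: 48.4% | m = 0.550: 38.4% | m = 0.525: 29.2% |
| 20% | m = 0.560: 42.4% | m = 0.520: 27.5% | m = 0.480: 15.8% |

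One pretreated subject in 25 (s = 4%) with r = 35% gives m = 0.590 and 54.5%.

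A second model keeps the same 21-point gain (60% − 39%) for everyone and lets q be the pretreated ORR on available treatment. With s = 20% and q of 20% to 30% (assumed), the blended comparator is 0.8 × 0.39 + 0.2 × q = 35.2% to 37.2%. Adding 21 points gives 56.2% to 58.2%, and the chance is 43.2% to 51.3%.

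**4. Effect when vidutolimod adds nothing.** With s = 20%:

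- q = 35%: blend 38.2%, P(X ≥ 15) = 2.2%.
- q = 20%: blend 35.2%, P(X ≥ 15) = 1.0%.
- q = 45% to 50%: blend 40.2% to 41.2%, P(X ≥ 15) = 3.6% to 4.5%.

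Against 2.7% for a pure first-line cohort, a lower pretreated ORR makes the comparison conservative. Only a pretreated ORR above the benchmark would raise the chance of a misleadingly good result.

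**5. Cohort D, side by side.** Section 1.3.3.1 names hedgehog inhibitors, and cemiplimab after them, as the systemic options for advanced BCC. Section 3.5 bars both classes. The 50% benchmark sits within the 48–56% that Section 1.3.3.1 gives for hedgehog inhibitors in pivotal studies. What remains is the phrase newly diagnosed, present in Section 3.1 and absent elsewhere.

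**The case against.** The best case for the plan is that Cohort E's operative text is consistent: synopsis, Section 3.1, Section 3.5 and SAP Section 2.1 agree. Newly diagnosed appears only in the background, and the same background section contrasts PD-1-refractory with immunotherapy-naive patients, which is the line Section 3.5 draws. This stands in part. The eligibility rules do not conflict with one another; the mismatch is between the rules and the stated rationale and apparent benchmark.

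The affected group may also be small. Sections 1.3.2 and 1.3.4.2 note that cemiplimab is approved first-line for PD-L1-high NSCLC, so chemotherapy for advanced disease without any anti-PD-1/PD-L1 agent may be uncommon. That stands: nothing in the documents shows that such subjects would reach 10% to 30% of the cohort.

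The study is exploratory (Section 8.1), SAP Section 1.2 states no formal hypothesis, and Table 12 is conditional rather than a success rule. That stands, and it limits the consequence. A descriptive comparison with a benchmark still needs matching populations.

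Finally, prior lines of therapy are summarised (Protocol Section 8.4.5, SAP Section 6.2), and SAP Section 7.2.1 lists prior therapy as an ORR subgroup. This helps only partly: the subgroup is optional, prior therapy is undefined, and the main estimate stays mixed.

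**Conclusion.** The gap in Cohort E is real and worth closing. As written, the plan can admit subjects to whom its only comparator does not apply, which weakens the comparison. Two things are inferred or assumed: the link from 39% to newly diagnosed disease rests on the roughly 40% in Section 1.3.3.3, and the losses in the working rest on assumed shares and response rates. The loss runs from about 4 percentage points (58.6% to 54.5%) at the mild end of the range to about 43 (58.6% to 15.8%) at the severe end.

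Three stronger readings are tempting, and the documents support none of them:

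- A reader might infer that the benchmark comparison is broken. The extent of any mixing is unknown and could be negligible.
- A reader might infer a risk of false success. If pretreated subjects respond less well, the bias runs the other way, with 2.7% falling to 2.2–1.0% at a 20% share.
- A reader might infer that Cohort D has the same problem. Both systemic classes the protocol describes for BCC are already barred, so the practical effect there is probably small and the matter is mainly one of wording.

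**What to change.** **Cohort E eligibility.** In Section 3.5, the synopsis, Section 3.1 and SAP Section 2.1, add: *and have not received prior systemic therapy for advanced or metastatic NSCLC*. This mirrors A1, B1 and F. If the sponsor does want chemotherapy-pretreated subjects, the alternative is to restate the Cohort E population in Section 1.3.3.3 and match the Table 12 benchmark to it. In either case, cite the source of the 39%.

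**Subjects already enrolled.** In SAP Section 7.2.1, change the prior-therapy ORR subgroup from *may* to *will* for Cohort E, and define it as prior systemic therapy for advanced disease, yes or no.

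**Cohort D.** Decide whether newly diagnosed is intended, then make Section 3.1 agree with Section 3.5, the synopsis and SAP Section 2.1.

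**Cost.** Wording in the next amendment, and one subgroup table from prior-treatment data already collected under Section 6.1.7. A few pretreated subjects become ineligible. The Table 12 thresholds do not change.

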3.6. Subject Exclusion Criteria

Subjects presenting with any of the following will not qualify for entry into the study:

1. Received radiation therapy (or other non-systemic therapy) within 2 weeks before first dose of study treatment on W1D1. Subjects should have recovered (i.e. Grade \leq 1 or at baseline) from radiation-related toxicities.
2. Treatment with complementary medications (e.g. herbal supplements or traditional Chinese medicines) to treat the disease under study within 2 weeks prior to start of study treatment or at any time during the treatment phase of the study. Refer to Section 3.8 for prohibited treatments.
3. Received systemic pharmacologic doses of corticosteroids > 10 mg/day prednisone within 15 days before first dose of study treatment on W1D1.
 - a. Subjects who are currently receiving steroids at a prednisone-equivalent dose of ≤ 10 mg/day do not need to discontinue steroids prior to enrollment.
 - b. Replacement doses, topical, ophthalmologic, and inhalational steroids are permitted.
 - c. Stress-dose corticosteroids will be required in subjects with adrenal insufficiency (see Section 4.1.1.1.1).
4. History of immune-mediated AE leading to permanent discontinuation due to prior PD1-blocking antibody.
5. Not fully recovered from AEs due to prior treatment (to Grade 1 or less, per CTCAE), with the exception of persistent vitiligo, alopecia, hypothyroidism, diabetes mellitus, and adrenal and/or pituitary insufficiency.

NOTE: Subjects previously treated with a CTLA-4-blocking antibody, subjects receiving corticosteroids with daily doses > 5 mg and ≤ 10 mg of prednisone equivalent for > 2 weeks, and subjects with clinical symptoms and/or laboratory findings suggesting risk for adrenal insufficiency should undergo diagnostic tests for adrenal insufficiency via local laboratory.

6. Active pneumonitis or history of noninfectious pneumonitis that required steroids.
7. Severe uncontrolled medical disease within 12 months of Screening, including but not limited to poorly controlled hypertension, unstable angina, myocardial infarction, congestive heart failure (New York Heart Association Class II or greater), pericarditis, cerebrovascular accident, or implanted or continuous use of a pacemaker or defibrillator, or emphysema with FEV1 $\leq 50\%$ predicted.
8. Known history of immunodeficiency.
9. Known additional malignancy that is progressing or required active treatment within the past 3 years. Exceptions include cancers that have undergone potentially curative therapy,

e.g. basal cell carcinoma of the skin, squamous cell carcinoma of the skin, localized prostate cancer with prostate-specific antigen level below 4.0 ng/mL, in situ cervical cancer on biopsy or a squamous intraepithelial lesion on Papanicolaou smear, and thyroid cancer (except anaplastic), in situ breast cancer, and adjuvant hormonal therapy for breast cancer > 3 years from curative-intent surgical resection.

10. Active autoimmune disease that required systemic treatment in past 2 years; replacement therapy is not considered a form of systemic treatment.
11. Untreated, symptomatic, or enlarging central nervous system (CNS) metastases or carcinomatous meningitis (including leptomeningeal metastases from solid tumors).
12. Prior allogenic tissue/solid organ transplant.
13. Active infection requiring systemic therapy.
14. Known or suspected active infection with severe acute respiratory syndrome coronavirus 2 (SARS-CoV-2).
15. Known or suspected active infection with human immunodeficiency virus, hepatitis B virus, or hepatitis C virus (testing is not required unless suspected).
16. Received a live virus/attenuated vaccination within 30 days before first dose of study treatment on W1D1.
17. Received blood products (including platelets or red blood cells) or colony stimulating factors (including granulocyte colony stimulating factor, granulocyte/macrophage colony stimulating factor, or recombinant erythropoietin) within 3 weeks before the W1D1 visit.
18. History of permanent discontinuation of cemiplimab due to infusion reactions or hypersensitivity to the investigational agents or their excipients.
19. Any concurrent uncontrolled illness, including mental illness or substance abuse, which in the opinion of the Investigator would make the subject unable to cooperate or participate in the study.
20. Participation in another clinical study of an investigational anticancer therapy or device within 30 days before first dose of study treatment on W1D1. Note: Participation in the follow-up phase (receiving no study treatment) of a prior study is allowed.
21. Requires prohibited treatment (i.e. non-protocol specified anticancer pharmacotherapy, surgery, or conventional radiotherapy) for treatment of malignant tumor.
22. Has a life expectancy of less than 3 months and/or has rapidly progressing disease (e.g. tumor bleeding, uncontrolled tumor pain) in the opinion of the treating Investigator.
23. Received previous vidutolimod treatment.
24. Pregnant or breastfeeding or expecting to conceive children within the projected duration of the study, from the time of consent until at least 150 days after last dose of study treatment.
25. Sexually active men and women of childbearing potential* who are unwilling to practice highly effective contraception prior to the initial dose/start of the first treatment, during the

study, and for at least 6 months after the last dose. Highly effective contraceptive measures include:

- Stable use of combined (estrogen and progestogen containing) hormonal contraception (oral, intravaginal, transdermal) or progestogen-only hormonal contraception (oral, injectable, implantable) associated with inhibition of ovulation initiated 2 or more menstrual cycles prior to screening
- Intrauterine device (IUD); intrauterine hormone-releasing system (IUS)
- Bilateral tubal ligation/occlusion
- Vasectomized man or partner, and/or
- Sexual abstinence†, ‡.

*Postmenopausal women must be amenorrheic for at least 12 months in order not to be considered of childbearing potential. Pregnancy testing and contraception are not required for women with documented hysterectomy.

†Sexual abstinence is considered a highly effective method only if defined as refraining from heterosexual intercourse during the entire period of risk associated with the study treatments.

‡Periodic abstinence (calendar, symptothermal, post-ovulation methods), withdrawal (coitus interruptus), spermicides only, and lactational amenorrhea method (LAM) are not acceptable methods of contraception. Female condom and male condom should not be used together.

26. Had major surgeries (including complete oncologic resection) within last 4 weeks prior to enrollment, and/or have not recovered adequately from the toxicities and/or complications from the intervention. Minor surgeries (including routine resections of early stage CSCCs and BCCs that may be due to field cancerization) require a 7-day washout.

